11.10. Subgroup and Sensitivity Analyses

Subgroup analyses are planned to be performed according to disease duration (≤ 2 and > 2 years) and pre-treatment (systemic naïve/experienced, biologic naïve/experienced) for all endpoints.

Sensitivity analyses are planned to be performed with respect to the applied statistical procedure (see Section 11.9) and by applying different imputation rules for missing data (see Section 11.11).

Additional subgroup analyses, eg. age, gender, baseline PASI, and sensitivity analyses may be performed and will be specified in the SAP. Multiple logistic regression analysis may be used to investigate the relationship between potential prognostic or risk factors and a single binary outcome variable (eg, influence of age or PK-level on SRe in Study Part 1).

11.11. Handling of Missing Data

All available data will be included in the analyses and will be summarized as far as possible. If not otherwise specified, there will be no substitution of missing data, ie, missing data will not be replaced, missing data will be handled as 'missing' in the statistical evaluation ('observed cases analysis').

Non-responder imputation will be applied for subjects with missing data for the primary endpoint at week 68 as described below:

Subjects who do not maintain control of disease (absolute PASI score ≥ 3) or subjects who discontinue study treatment during the study before week 68 will be considered non-responders for the primary endpoint at week 68. In addition, subjects who do not return for evaluation at week 68 will be considered non-responders at week 68.

Non-responder imputation for the other binary endpoints will be performed analogously.

For continuous response parameters, the last available observation after baseline will be calculated and used for analysis in case of premature termination (Last Observation Carried Forward approach; LOCF).

LOCF may also be used as sensitivity analysis for binary response parameters. Treatment failure rules (TFR) will be applied after week 68 for a separate analysis. Additional sensitivity analyses may be done by applying different imputation rules for missing data (eg, 'multiple imputation'). An 'observed cases analysis' for all binary and continuous endpoints without substitution of missing data may also be used. A more detailed description of the handling of missing data will be provided in the SAP.

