8. CONCOMITANT THERAPY

Concomitant therapies will be recorded until week 220 for subjects participating in all three study parts. For subjects of the re-treatment arm concomitant therapies will be recorded until 12 weeks after the last dose of study drug. For subjects not participating in Study Part 3, concomitant therapies should be recorded beyond week 72 only in conjunction with related serious adverse events (SAEs) that meet the criteria outlined in Section 12.3.2. All therapies (prescription or over-the-counter medications, including vaccines, vitamins, herbal supplements) different from study drug, as well as all shampoos, moisturizers or emollients used to treat psoriasis, must be recorded in the CRF. Modification of an effective preexisting therapy should not be made for the explicit purpose of entering a subject into the study.

If a prohibited therapy is administered during the (blinded) active treatment phase (ie, week 0 to week 68 – all subjects, whether SRe or not and re-treatment arms), discontinuation should be discussed with the Sponsor. If a prohibited therapy is initiated during weeks 68 to 220 (only SRe), the subject should still complete the final visit at week 220, and the medication should be recorded as a concomitant medication.

For non-SRe: If a prohibited therapy is initiated after the final efficacy assessments at week 68 and until the end of the safety follow-up at week 72, the subject should still complete the final safety follow-up visit at week 72 and the medication should be recorded as a concomitant medication.

The Sponsor must be notified in advance (or as soon as possible thereafter) of any instances in which prohibited therapies are administered.

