10.2. Discontinuation of Study Treatment

A subject will not be automatically withdrawn from the study if he or she has to discontinue treatment before the end of the treatment regimen.

A subject's study treatment must be permanently discontinued if:

- The investigator believes that for safety reasons or tolerability reasons (eg, AE) it is in the best interest of the subject to discontinue study treatment.
- The subject shows no response to study treatment at week 28, defined as no change or worsening of PASI score at week 28 in comparison to week 0.
- The subject becomes pregnant.
- The subject is diagnosed with a malignancy, with the exception of no more than 2 localized basal cell skin cancers that are treated with no evidence of recurrence or residual disease.
- The subject is deemed ineligible according to the following TB screening criteria:
 - A diagnosis of active TB is made.
 - A subject has symptoms suggestive of active TB based on follow-up assessment questions and/or physical examination or has had recent close contact with a person with active TB and cannot or will not continue to undergo additional evaluation.
 - A subject undergoing evaluation has a chest radiograph with evidence of current active TB and/or a positive QuantiFERON-TB Gold test result and/or an indeterminate QuantiFERON-TB Gold test result on repeat testing (refer to Section [9.6](#)) (and/or a positive tuberculin skin test result in countries in which the QuantiFERON-TB Gold test is not approved/registered or the tuberculin skin test is mandated by local health authorities). Indeterminate QuantiFERON-TB Gold test results should be handled as described in Section [9.6](#).

- A subject receiving treatment for latent TB discontinues this treatment prematurely or is noncompliant with the therapy.
- A subject receiving treatment for latent TB discontinues this treatment prematurely or is noncompliant with the therapy.
- The subject initiates a protocol-prohibited medication, eg, for a worsening of his or her psoriasis (unless agreed to by the medical monitor).
- The subject withdraws consent for administration of study drug.
- The subject is unable to adhere to the study visit schedule or comply with protocol requirements.
- The subject develops an allergic reaction such as bronchospasm with wheezing and/or dyspnea requiring ventilatory support, or symptomatic hypotension that occurs following a study drug administration.

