11.2. Sample Size Determination

This randomized, double-blind, parallel-group, multicenter phase 3b trial is designed to demonstrate that guselkumab 100 mg q16w treatment is non-inferior to guselkumab 100 mg q8w treatment in SRe as assessed by the proportion of subjects with an absolute PASI score <3 at week 68. A non-inferiority margin of 10% was chosen based on a minimally clinically meaningful difference. This margin was also used in CNTO1959PSO3009 (ECLIPSE) study and is therefore considered a valid approach for evaluating non-inferiority of a new treatment.

The null hypothesis H_0 and the alternative hypothesis H_A are formulated as follows:

- $H_0: P_T - P_S \leq -10\%$ ('inferiority')
- $H_1: P_T - P_S > -10\%$ ('non-inferiority')

where P_T and P_S denote the proportions of subjects with an absolute PASI score <3 at week 68 in the guselkumab 100 mg q16w treatment arm (P_T = proportion test treatment) and the guselkumab 100 mg q8w treatment arm (P_S = proportion standard treatment).

Based on data from CNTO1959PSO3002 the proportion of subjects with an absolute PASI score <3 at week 68 is assumed to be 90% for guselkumab 100 mg q8w. The expected difference in proportions between the treatment groups (guselkumab 100 mg q16w minus guselkumab 100 mg q8w) is 0%.

According to current international guidance documents ([CPMP, Points to consider on switching between superiority and non-inferiority 2001](#)) the intent-to-treat analysis set and the per-protocol analysis set should have equal importance in a non-inferiority trial and their use should lead to similar conclusions for a robust interpretation.

Therefore, the sample size estimation using the power approach is performed for the per-protocol analysis set as described below. No formal adjustment of the significance level is necessary ([CPMP, Points to Consider on Multiplicity Issues in Clinical Trials 2002](#)).

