When the sample size in each group is 112, a two-group large-sample normal approximation Wald Z-test of proportions with a one-sided 0.05 significance level will have 80% power to reject the null hypothesis that the guselkumab 100 mg q16w treatment is inferior to the guselkumab 100 mg q8w treatment (the difference in proportions, $P_T - P_S$, is $\leq -10\%$) in favor of the alternative hypothesis that the guselkumab 100 mg q16w treatment is non-inferior to the guselkumab 100 mg q8w treatment (the difference in proportions is $> -10\%$), assuming that the expected difference in proportions is 0 and the proportion in the guselkumab 100 mg q8w treatment group is 90% (nQuery Advisor® 7.0).

Considering routine clinical conditions it is assumed that a rate of about 20% randomized subjects will not be evaluable for the per-protocol analysis in Study Part 2. Thus, 280 subjects (140 subjects per treatment group) are planned to be randomized in a ratio of 1:1 to meet the required sample size of 224 subjects (112 subjects per treatment group) for the per-protocol analysis.

Based on data from CNTO1959PSO3001 and CNTO1959PSO3002, it is anticipated that approximately 35% of enrolled subjects in Study Part 1 will be eligible for randomization at week 28 in Study Part 2. Thus, a total of 800 subjects should be enrolled in Study Part 1 to ensure that at least 280 subjects are eligible for randomization in Study Part 2. Accounting for a 10% drop-out rate of subjects ineligible for randomization at week 28 because of study discontinuation prior to week 28, it is therefore planned to enroll a total of 888 subjects in Study Part 1.

Note: Screenings and enrollments will be adjusted if necessary (without protocol amendment) to achieve 280 SRe at week 28. Ongoing subjects in Study Part I will continue to Part II if eligible, irrespective of whether or not 280 SRe are already randomized. Only screenings will be closed.

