11.3. Efficacy Analyses

Analysis Data Set

The efficacy analyses will be performed separately for each Study Part. For all efficacy analyses to compare guselkumab 100 mg q16w vs. guselkumab 100 mg q8w in Study Part 2, all randomized subjects at week 28 will be included.

In Study Part 2 subjects will be analyzed according to the treatment group to which they were randomized regardless of the treatment they actually received (intent-to-treat analysis set).

The per-protocol analysis set will consist of all subjects in the intent-to-treat analysis set terminating the study without any major deviation of the protocol and its procedures. Subjects with major protocol deviations will be excluded from the per-protocol analysis.

The confirmatory analysis of the primary endpoint variable will be performed both for the intent-to-treat analysis set and the per-protocol analysis set.

In Study Part 1 and Study Part 3 all subjects treated with at least one dose of study drug will be included in the efficacy analyses. For all efficacy analyses in Study Part 1 and Study Part 3, subjects will be analyzed according to the treatment they actually received.

Primary Endpoint

The proportion of subjects with an absolute PASI score <3 at week 68 will be displayed in a frequency table providing the number and percentage of subjects. Graphical presentation will be presented by means of a bar chart.

To test the non-inferiority of guselkumab 100 mg q16w to guselkumab 100 mg q8w with a non-inferiority margin of 10% in Study Part 2, a one-sided ($\alpha=0.05$) two-group large-sample normal approximation Wald Z-test with Mantel-Haenszel stratum weights for 'disease duration' will be used. The Mantel-Haenszel estimate, the two-sided 90% Wald-type confidence limits, and the test for the difference of proportions will be computed by using Mantel-Haenszel stratum weights ([Mantel und Haenszel 1959](#)) and the Sato variance estimator ([Sato 1989](#)). Non-inferiority will be accomplished when the lower limit of the two-sided 90% confidence interval for the difference in response rates (guselkumab 100 mg q16w minus guselkumab 100 mg q8w) will be $> -10\%$ both for the intent-to-treat analysis and the per-protocol analysis.

Non-responder imputation will be applied for subjects with missing data for the primary endpoint as described in Section [11.11](#).

Major Secondary Endpoints

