In Study Part 2 the two-group large-sample normal approximation Wald Z-test with Mantel-Haenszel stratum weights for 'disease duration' will be used to compare the proportion of subjects responding to treatment. The Mantel-Haenszel estimate, the two-sided 90% Wald-type confidence limits, and the test for the difference of proportions in Study Part 2 will be computed by using Mantel-Haenszel stratum weights ([Mantel und Haenszel 1959](#)) and the Sato variance estimator ([Sato 1989](#)). Continuous response parameters in Study Part 2 will be compared using an analysis of variance model with fixed effects for treatment group and disease duration and baseline value as covariate. Time-to-event endpoints will be analyzed using Kaplan-Meier product limit methods to estimate the survival distributions and the median time-to-event. Exploratory statistical analyses of response parameters in Study Part 1 and Study Part 3 will be performed analogously, as appropriate. Details will be provided in the SAP.

Non-responder imputation (for binary endpoints) or Last Observation Carried Forward (LOCF) imputation (for continuous endpoints) will be applied for subjects with missing data for the other secondary endpoints as described in Section [11.11](#).

Criteria for Endpoints

Treatment failure: Subjects who discontinue study agent due to lack of efficacy, an AE, worsening of psoriasis, or who started a protocol-prohibited medication/therapy during the study period that could improve psoriasis are considered treatment failures. Treatment failure rules (TFR) will be applied after week 68 for a separate analysis. The treatment failure rules will be documented in detail in the SAP.

PASI 75 Responders:	Subjects with $\geq 75\%$ improvement in PASI from baseline at week 28
PASI 90 Responders:	Subjects with $\geq 90\%$ improvement in PASI from baseline at week 28
PASI 100 Responders	Subjects with 100% improvement in PASI from baseline at week 28
Maintenance of control of disease	Subjects with a PASI score < 3
Fluctuating disease:	absolute PASI score 3 to 5
Loss of disease control	absolute PASI score > 5

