5.1.8. Missing Data Imputation

Data of study endpoints from subjects who started a protocol-prohibited medication/therapy during the study period that could improve psoriasis will be set to 'missing' from that point onward. The protocol-prohibited medications/therapies are listed in section 8.1 of the CSP. For the statistical analysis of Study Part 3, protocol prohibited medication/therapy will be identified in the SDTM DV domain as DVDECOD='RECEIVED DISALLOWED CONCOMITANT TREATMENT'.

After the rule for handling of protocol-prohibited medication/therapy is applied, missing data will be handled as follows:

- Non-responder imputation for binary efficacy endpoints will be applied for subjects with missing data at any study visit.
- Last Observation Carried Forward (LOCF) imputation for continuous efficacy endpoints will be applied for subjects with missing data in Study Part 3.
 - This approach implies that a separate "endpoint" visit will be calculated that gets the imputed value, thus leaving the observed value as it is, if data are summarized descriptively only.
 - The earliest visit used for LOCF approach is the week 68 visit; no data from Parts 1 and 2 will be used as LOCF value for the week 116/164/220 visit.

- Time-to-event analyses of binary endpoints will be performed after the rule for handling of protocol-prohibited medication/therapy is applied (missing data will not be replaced for time-to-event analyses).

An 'observed cases analysis' for all binary and continuous endpoints in Study Part 3 without any imputation of missing data (ie, also not set to missing once protocol-prohibited medication/therapy is started) will also be done. These analyses will provide only descriptive statistical results and will also include by-visit data of Study Parts 1 and 2 (see section 5.6).

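### The week-68 non-responder rule leaves uncovered those subjects who start a prohibited psoriasis therapy in Part 2 without being recorded as having discontinued study treatment

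*Protocol*

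**What the plan says.** **Primary rule.** Section 11.11 gives three routes to non-response at week 68: PASI of 3 or more, no week-68 evaluation, and treatment discontinuation ("subjects who discontinue study treatment during the study before week 68 will be considered non-responders for the primary endpoint at week 68"). More detail is deferred to the SAP.

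**Treatment failure.** Section 11.3 counts starting a prohibited therapy that could improve psoriasis as treatment failure, but limits its use: "Treatment failure rules (TFR) will be applied after week 68 for a separate analysis". Section 11.11 repeats the limit.

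**Handling of prohibited therapy.** Section 10.2 lists it among the grounds for permanent discontinuation: "The subject initiates a protocol-prohibited medication, eg, for a worsening of his or her psoriasis (unless agreed to by the medical monitor"). Section 8, for weeks 0 to 68, says only that "discontinuation should be discussed with the Sponsor". Section 9.1.4 puts the last injection at week 60 and the final assessments at week 68.

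**Success criterion.** Section 11.3 requires the lower 90% confidence limit to exceed -10% in both the ITT and the per-protocol set. It adds: "Subjects with major protocol deviations will be excluded from the per-protocol analysis". The protocol does not define a major deviation. Appendix 4 of the Part 3 SAP and of the re-treatment SAP lists disallowed concomitant treatment as one.

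**Later phases.** Under Section 5.1.8 of the Part 3 SAP, "Data of study endpoints from subjects who started a protocol-prohibited medication/therapy during the study period that could improve psoriasis" are set to missing from that point, and missing binary outcomes become non-response. The re-treatment SAP does the same for its efficacy endpoints. Neither SAP governs the primary analysis.

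**The concern.** A subject who flares, uses a prohibited therapy and returns at week 68 with PASI below 3 has not kept control on the assigned regimen alone. If nobody records a discontinuation of study treatment, Section 11.11 scores that subject as a responder. If the Appendix 4 list also applied in Part 2, the per-protocol analysis removes the subject. The failure is then counted in neither confirmatory analysis, and agreement between the two gives no reassurance.

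The direction depends on which arm has more such subjects. Under Section 6 the last active dose is at week 52 in q16w and week 60 in q8w. Weeks 60 to 68 are therefore weeks 8 to 16 after active drug in q16w, and weeks 0 to 8 in q8w. More use in q16w is plausible, though the documents do not show it. If so, both analyses lean towards declaring q16w non-inferior.

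**Working it through.** **1. Which users are uncovered**

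| Course after starting prohibited therapy | Status at week 68 if PASI is below 3 |
|---|---|
| Study treatment discontinued under 10.2 | Non-responder under 11.11 |
| Continued with medical monitor agreement (10.2), or after the Section 8 discussion | Responder: no route in 11.11 applies |
| Started after the week-60 injection | Responder unless a discontinuation is recorded, although no dose is left to stop |

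The gap is the last two rows.

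**2. The plan's own figure**

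Inputs from Section 11.2: "one-sided 0.05 significance level will have 80% power to reject the null hypothesis"; "the proportion of subjects with an absolute PASI score <3 at week 68 is assumed to be 90% for guselkumab 100 mg q8w"; expected difference 0; margin 10 points.

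n = (1.645 + 0.842)² × (0.9×0.1 + 0.9×0.1) / 0.10² = 6.18 × 18 = 111.3, so 112 per arm (power 80.2%). With 20% not evaluable, 112/0.80 = 140 per arm. The stated design reproduces.

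**3. Effect on the false-positive rate**

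The documents give no rate of prohibited therapy, so it is assumed. Let f be the share of the q16w arm whose failure is turned into PASI below 3 by an uncovered use, with none in q8w. Set the true rates, with users counted as failures, on the margin: 80% q16w, 90% q8w.

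- ITT response counted in q16w: 0.80 + f.
- Per-protocol response in q16w with users removed: 0.80/(1 - f).
- Test: unstratified Wald, lower two-sided 90% limit above -10%. The Mantel-Haenszel stratification is not modelled.
- ITT alone (140 per arm) and per-protocol alone (112 per arm): exact binomial enumeration.
- Both together: simulation in which the per-protocol set loses the users plus a random 20%.

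| f | ITT rate counted | PP rate counted | ITT alone | PP alone | Both succeed |
|---|---|---|---|---|---|
| 0 | 80% | 80.0% | 5.2% | 5.3% | 3.3% |
| 1% | 81% | 80.8% | 8.3% | 7.4% | 5.2% |
| 2% | 82% | 81.6% | 12.8% | 10.2% | 7.8% |
| 3% | 83% | 82.5% | 18.8% | 14.0% | 11.5% |

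The last column is the relevant one, because the protocol requires both. In 140 subjects, 1%, 2% and 3% are 1.4, 2.8 and 4.2 subjects. With users counted as non-responders in both sets, the true rates stay at 80% and 90%, so the joint rate stays at about 3.3%.

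**4. How few subjects can matter**

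Take 126/140 (90%) in q8w. With 121/140 in q16w, the difference is -3.57 points, the standard error is √(0.864×0.136/140 + 0.9×0.1/140) = 0.0385, and the lower limit is -3.57 - 1.645×3.85 = -9.9 points: pass. With 120/140 the lower limit is -10.7 points: fail. Near that threshold one reclassified subject changes the ITT result.

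**The case against.** Much of the case on the other side stands.

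- **Most users are already failures.** A reader might infer that any user of prohibited therapy with PASI below 3 is an ITT responder. The documents do not support that: discontinuation is the default in Section 10.2, and Section 11.11 turns it into non-response. Section 9.1.4 also sends such subjects to a safety follow-up visit, although it assigns no response status.
- **The Part 2 SAP is not among the documents.** Section 11.11 defers detail to the SAP, and the supplied SAPs say each analysis has its own. One cannot conclude that the confirmatory endpoint was analysed under a weaker rule than the later phases, only that the protocol text is weaker.
- **Group 2d.** A reader might extend the gap to subjects re-treated in Part 2. That is unlikely to hold. They had PASI above 5, the re-treatment SAP describes their randomized treatment as stopped, and their schedule has no week-68 visit. The overall safety SAP counts three of them.
- **Removal from the per-protocol set is an inference** from deviation lists written for other phases.
- **The scenario sits on the margin.** The overall safety SAP reports 297 randomized subjects and 273 entering withdrawal, which under the design requires PASI below 3: 273/297 = 92%. True rates of 80% and 90% imply about 85%, or 252 of 297. Reaching 273 would need some 20 of about 45 failures to be rescued, and nothing suggests that. The table shows what the rule permits, not what happened.
- **The primary analysis is complete** (Section 1 of the SAPs), and the sponsor was to be unblinded for it. Replacing the primary rule now would be post hoc.

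None of this covers agreed continuation or starts in weeks 60 to 68.

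**Conclusion.** The gap is real but narrow: a cheap improvement, not a defect that undermines the trial. As the protocol is written, a subject who starts a prohibited psoriasis therapy in Part 2, has no recorded discontinuation of study treatment and reaches PASI below 3 at week 68 is an ITT responder.

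The joint false-positive rate goes from about 3.3% to 5.2%, 7.8% or 11.5% when 1%, 2% or 3% of q16w subjects are affected, so it exceeds the nominal 5% only slightly at 1% and clearly from 2%. This assumes that use is confined to q16w, that true response lies on the margin, that users leave the per-protocol set, and that other per-protocol loss is random. If use were equally frequent in both arms, the bias would be smaller. The ITT-alone figures overstate the risk, because success needs both sets.

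The conclusion concerns the protocol text. If the Part 2 SAP already treats prohibited therapy as non-response, only the wording of Section 11.11 remains to be aligned.

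**What to change.** - **Rule.** In Section 11.11, and in the Part 2 SAP if it lacks the rule, state that starting a Section 8.1 therapy that could improve psoriasis, at any time from week 28 to the week-68 assessment, counts as week-68 non-response whatever PASI is observed. This matches what the Part 3 SAP achieves for later endpoints. State that entry into group 2d also counts.
- **Analysis.** Unless the Part 2 SAP already had the rule, report it as a sensitivity analysis of the primary endpoint: in ITT, and in the per-protocol set with these subjects kept as non-responders. Give the number affected per arm.
- **Consistency.** Sections 8 and 10.2 describe different handling of a subject who starts prohibited therapy and must be reconciled.

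**Cost.** One re-derived binary variable, from concomitant-medication and deviation data already collected. Response rates may fall slightly. Suppose both arms show 90% with users counted as responders. If users occur only in q16w, ITT power at 140 per arm falls from 87.4% to 79.2%, 69.0% or 57.7% with 1%, 2% or 3% users. Part of that fall reflects a true difference between arms that the present rule would hide. If use is equal in both arms, power is 84.8%, 82.4% or 80.0%. The planned sample size does not change.
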